2.2 Investigational Agent

2.2.1 J591

The J591 Mab is a deimmunized monoclonal antibody directed at the extracellular domain of human PSMA. J591 was derived from murine J591 using Biovation's (Biovation, Aberdeen, Scotland, UK) DeImmunisation technology in which individual amino acids in predicted B and T cell epitopes were replaced with other amino acids such that the epitope would no longer be recognized by the human immune system, thereby decreasing the likelihood of the development of an anti-mAb antibody response in humans.²⁸ This results in a potentially non-immunogenic antibody, which might be administered to patients on multiple occasions over long periods without inducing an immune response (see Clinical Experience). Furthermore, the deimmunized Mab additionally has been engineered to possess the effect of inducing antibody dependent cellular cytotoxicity (ADCC) with human immune effector cells.

J591 is produced from NS0 cells by Lonza (Lonza Biologics, Slough, UK). The molecular weight of J591 is approximately 147,000 daltons as determined by Matrix Assisted Laser Desorption Mass Spectrometry (MALDI-TOF). The naked antibody is formulated in a 50 mM sodium phosphate, pH 5.5, containing 100 mM sodium chloride and 2 mM EDTA at a nominal concentration of 5 mg/mL.

2.2.2 DOTA-J591

In order to radiolabel J591 with β^- emitting radionuclides such as ^{177}Lu , the J591 antibody molecule is first conjugated to a macrocyclic chelating agent, 1,4,7,10-tetraazacyclododecane- N,N',N'',N'''-tetraacetic acid (DOTA) by direct coupling of one of the four carboxylic acid groups of DOTA to the primary amines present in the protein structure.

The DOTA conjugated antibody is formulated in 0.3 M ammonium acetate, pH 7.0 at a nominal concentration of 8 mg/mL.

2.2.3 Radiolabeled J591

The DOTA-J591 antibody molecule is labeled with radiometal ^{177}Lu or ^{111}In in 1.0 M ammonium acetate buffer at pH 7.0. The radiolabeled J591 complex is then purified using size-exclusion column chromatography.

To avoid the effects of autoradiolysis on the antibody, reaction time is minimized and the radiolabeled antibody preparations are formulated in phosphate buffered saline containing not more than 1% Human Serum Albumin (HSA). All reagents used in the conjugation and purification of J591 are made with pyrogen-free water. Radiolabeled J591 is periodically tested for sterility and pyrogenicity.

Each patient dose will be supplied to the study site on the day of or day before treatment by the central radiopharmacy.

The J591 mAb is a deimmunized monoclonal antibody directed at the extracellular domain of human PSMA. For additional details, see Section 1 and/or Investigator Brochure.

Radiolabeled antibody preparations are formulated in phosphate buffered saline containing not more than 1% Human Serum Albumin (HSA).

In order to radiolabel J591 with β^- emitting radionuclides, the antibody molecule is first conjugated to a macrocyclic chelating agent, 1,4,7,10-tetraazacyclododecane- N,N',N'',N'''-tetraacetic acid (DOTA) by direct coupling of one of the four carboxylic acid groups of DOTA to the primary amines present in the protein structure.

The radiolabeling of J591 with ^{177}Lu is achieved by adding the radionuclide to the ammonium acetate buffered J591. To avoid the effects of autoradiolysis on the antibody, reaction time is minimized and the reaction mixture is purified with a size exclusion column prior to administration.

All reagents used in the conjugation and purification of J591 are made from pyrogen-free water. Radiolabeled J591 is tested periodically for sterility and pyrogenicity. Refer to the Investigator Brochure for further details.

2.2.4 Pharmacokinetics

The pharmacokinetics of J591 antibody was studied in patients with prostate cancer using ^{111}In -J591 as a radiotracer. In a Phase 1 dose escalation study (see above) 4 groups of patients received different amounts of J591 antibody (25, 50, 100, 200 mg/m²) mixed with a trace amount of ^{111}In -J591 (5 mCi/1-2 mg). In a different Phase 1 dose-escalation study using ^{90}Y -J591 (see above), a group of patients received 20 mg of total J591 antibody mixed with a trace amount of ^{111}In -J591 (5 mCi/1-2 mg) for imaging studies prior to ^{90}Y treatment dose. These studies demonstrated that the plasma clearance kinetics of ^{111}In -J591 antibody is dose-dependent at low doses (<50 mg/m²). It should be noted that, in these studies, plasma clearance kinetics was determined based on the measurement of radioactivity in the plasma over time. The actual J591 antibody levels have not been measured; there is an assumption that the clearance of radiolabeled antibody does indeed reflect the J591 antibody clearance. The plasma clearance kinetics, based on bi-exponential fitting of plasma-time activity curves indicate that the terminal half-life ($T_{1/2\beta}$) is about 44.2 ± 13.9 hrs at 11 mg/m² antibody dose and 59.3 ± 16.6 hrs at 25 mg/m² antibody dose. At higher doses of antibody mass, the plasma clearance is relatively slower, but stable. In summary, the plasma clearance of antibody increases at lower doses of antibody (<25 mg/m²). In addition, repeat administration of J591 antibody over a 4-week period does not affect plasma clearance of radiolabeled J591 in patients with prostate cancer (data not shown).

In a Phase 1 dose-escalation study using ^{177}Lu -J591 (see above), a group of patients received J591 antibody mixed with a ^{177}Lu -J591 (10-70 mCi/m² and total J591 10mg/m²). The plasma clearance kinetics (shown in Table 1-2) demonstrate that there is no difference between ^{177}Lu and ^{111}In labeled J591 antibody.

Table 1-2: ^{177}Lu -J591 Vs. ^{111}In -hJ591: Plasma Clearance Kinetics

Pts.	mg/m ²	$T_{1/2\alpha}$ (hr)	$T_{1/2\beta}$ (hr)	V_d at T_0	Clearance
n=18[#]	10	3.61 ± 5.70	46.8±12	3949 ± 1067	72 ± 34
n=16[*]	11	2.37 ± 1.94	44.2±14	4042 ± 863	94 ± 34
n=3^{\$}	25	3.36 ± 2.17	59.3±17	3698 ± 224	56 ± 16
n=3^{\$}	50	7.83 ± 9.5	99.7±32	4156 ± 256	47 ± 6.7
n=3^{\$}	100	5.7 ± 7.5	105±38	4373 ± 566	40 ± 13

[#] = In a Phase 1 Dose escalation protocol, 18 patients were treated with ^{177}Lu -J591

^{*} = In a Phase 1 Dose escalation protocol, 16 Patients were treated with ^{90}Y -J591 and one week prior to treatment, ^{111}In -J591 kinetics were studied.

^{\$} = In a Phase 1 Dose escalation protocol with huJ591 cold antibody treatment, 3 patients in each group received different amounts of cold huJ591 mixed with ^{111}In -J591.

2.2.5 Biodistribution

The imaging studies with ^{111}In -J591 in patients with prostate cancer showed that liver is the principal organ with significant uptake of radiolabeled antibody. The liver uptake of J591 is a function of J591 antibody mass administered (Table 1-3): the higher the antibody mass, the lower the relative proportional uptake of radiolabeled antibody by the liver. In addition, at 20 mg of J591 administered in Phase 1 dose escalation trials with ^{111}In -DOTA-J591, the liver uptake increases with time and is at a maximum by day 6 ($27.0 \pm 1.7\%$ of injected dose). No significant localization was seen in other major organs, such as spleen and kidneys.

Biodistribution: ^{111}In -J591 vs. ^{177}Lu -J591

The imaging studies were done 5 times over a period of one week with ^{111}In and 2 weeks with ^{177}Lu . The uptake of radioactivity in various source organs (% injected dose/organ) was determined. The imaging studies clearly document that the *in vivo* distribution of radiolabeled J591 during the first week is quite similar with both ^{111}In and ^{177}Lu radionuclides (Table 1-4).

Table 1-3: ^{111}In -J591: Liver Uptake (% injected dose) as a Function of J591 Antibody Mass

Time	11 mg/m^2	25 mg/m^2	50 mg/m^2
1	13.1 ± 2.5	9.6 ± 1.0	7.9 ± 0.8
24	19.0 ± 3.2	12.9 ± 2.1	11.2 ± 1.2
48	20.8 ± 2.8	ND	11.0 ± 0.4
72	22.5 ± 2.4	14.5 ± 1.2	12.1 ± 1.0
120	24.6 ± 2.8	ND	ND
144	27.0 ± 1.7	17.1 ± 3.2	13.9 ± 1.0

Table 1-4: Biodistribution of Radiolabeled J591 Antibody

Organ	¹¹¹ In-J591		¹⁷⁷ Lu-J591		DAY 0	DAY 7
	DAY 0	DAY 6	DAY 0			
Whole Body	100.0 \pm 0.0	66.1 \pm 18.4			100.0 \pm 0.0	69.8 \pm 9.5
Remainder	52.3 \pm 5.7	24.9 \pm 16.8			57.5 \pm 6.4	34.7 \pm 6.9
Heart Contents	8.9 \pm 2.3	3.4 \pm 1.2			8.8 \pm 2.2	3.1 \pm 0.9
Kidneys	2.4 \pm 0.8	2.5 \pm 0.7			2.2 \pm 0.5	2.5 \pm 0.5
Liver	14.7 \pm 3.2	28.0 \pm 7.8			15.0 \pm 3.8	23.7 \pm 7.0
Lungs	9.0 \pm 2.0	4.4 \pm 1.7			6.9 \pm 1.9	3.1 \pm 0.7
Red Marrow	10.9 \pm 5.0	1.2 \pm 1.1			7.4 \pm 2.4	0.6 \pm 0.4
Spleen	1.8 \pm 0.6	1.7 \pm 0.8			2.2 \pm 1.0	2.1 \pm 0.8

2.2.6 Radiation Dosimetry

Based on imaging studies and plasma clearance with ¹⁷⁷Lu-J591, the residence times (τ) of radioactivity in various source organs (as shown in Table 1-4) were calculated. Using “S” factors from MIRD tables, radiation dosimetry (cGy/mCi) for ¹⁷⁷Lu-J591 was estimated (Table 1-5). Following administration of ¹⁷⁷Lu-J591, the liver is the critical organ, receiving 7.77 ± 2.23 rads/mCi, and the kidneys and spleen receive <7 rads/mCi. The bone marrow dose was estimated to be 1.17 ± 0.37 rads/mCi based on the assumption that 36% of bone marrow volume represents plasma volume.

Hematopoietic toxicity is usually the dose-limiting factor in RIT (54). Radiation dose of 9.0 Gy to the bone marrow is generally regarded as an “organ injury dose” and the tolerable absorbed doses were usually estimated to be 65% of LD50 (50%) organ injury dose. Therefore, the tolerable absorbed dose for bone marrow is about 3.0 Gy (330 rads). The maximum tolerable radiation doses to kidneys, liver and spleen are approximately 20-25 Gy (2000-2500 rads). Dosimetric studies using radiolabeled antibodies have been effectively used by many investigators to determine patient-specific radiation dosimetry of radiolabeled antibody treatment (55, 56). Based on the dosimetry data shown in Table 1-5, the maximum bone marrow dose following administration of 70mCi/m² of ¹⁷⁷Lu-J591 would deliver 164 rads to an average person with a BSA of 2.0 m². The maximum dose the liver would be about 1100 rads, well below the maximum tolerable liver dose.

Table 1-5: Radiation Dosimetry (rads/mCi) of ^{177}Lu -J591 in Patients with Prostate Cancer

Organ	Mean	S.D.
Adrenals	0.52	± 0.08
Brain	0.40	± 0.07
Gall Bladder	0.55	± 0.08
LLI Wall	0.42	± 0.07
Small Intestine	0.43	± 0.07
Stomach	0.45	± 0.07
ULI Wall	0.44	± 0.07
Heart Wall	3.50	± 0.70
Kidneys	5.20	± 1.29
Liver	7.77	± 2.23
Lungs	2.79	± 0.80
Muscle	0.42	± 0.07
Pancreas	0.52	± 0.08
Red Marrow	1.17	± 0.37
Bone Surfaces	0.70	± 0.14
Skin	0.42	± 0.07
Spleen	7.28	± 3.41
Testes	0.36	± 0.13
Thymus	0.44	± 0.07
Thyroid	0.41	± 0.07
Urin. Bladder Wall	0.97	± 0.22
Total Body	0.71	± 0.10
Effective Dose Equiv.	2.14	± 0.35
Effective Dose	1.33	± 0.19

2.3 Rationale

As stated above, we have validated that J591 can target known sites of disease and have preliminary evidence that there is anti-tumor effect of radiolabeled J591. Since forms of radiotherapy have been validated in the clinically localized as well as salvage setting, “targeted radiotherapy” in the form of radioimmunotherapy is at least theoretically an attractive option with the possibility being a higher yield therapy in the minimal disease (biochemical only) setting [see information on anti-CD20 based radioimmunotherapy above].

The objective of this study is to determine the efficacy of the addition of ^{177}Lu -J591 to ketoconazole in men with progressive biochemical (PSA) prostate cancer despite medical or surgical castration. All subjects will receive ketoconazole (400 mg p.o. TID) plus replacement doses of hydrocortisone (20 mg am, 10 mg pm). Subjects will be randomized to receive a single dose of 70 mCi/m² ^{177}Lu -J591 or trace-labeled ^{111}In -J591 (i.e. placebo). Subjects will be followed for response, disease progression, safety and toxicity. The treatment phase will last until progression of disease or toxicity necessitating discontinuation of therapy. Subjects will be followed until the primary endpoint, which is the development of radiographically apparent metastatic disease.

2.4 Correlative Studies Background

2.4.1 Adrenal androgen levels

Although androgen deprivation therapy with LHRH agonists are successful in suppressing testosterone levels in the majority of cases, adrenal androgen levels are not typically suppressed by significant amounts (57). In addition, some evidence exists that targeting adrenal androgens may play a role in the management of prostate cancer (58, 59), leading to the common use of ketoconazole for this purpose. CALGB 9583 was a randomized trial of antiandrogen withdrawal with or without ketoconazole (60). As part of the correlative sciences portion of this trial (secondary endpoint), adrenal androgen level were prospectively collected. Baseline adrenal androgen levels in men with metastatic castrate resistant prostate cancer were associated with PSA response and overall survival (61). Based upon these data, we plan to prospective assess and validate these results in men with biochemically progressive castrate resistant prostate cancer. As published we will compare the median baseline androgen levels in those with a PSA response vs those without. In addition, we will categorically analyze subsets of baseline adrenal androgen levels and correlate them with time to development of radiographically apparent metastatic disease and overall survival. As the published analysis did not prospectively identify categorical values for analysis (median levels were used), we will also use prospective determined levels based upon the published studies and categorize subsets for analysis.

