- 3.2.18 Other serious illness(es) involving the cardiac, respiratory, CNS, renal, hepatic or hematological organ systems which might preclude completion of this study or interfere with determination of causality of any adverse effects experienced in this study
- 3.2.19 Prior investigational therapy (medications or devices) within 4 weeks of treatment. Furthermore, other investigational therapy is not permitted during the treatment phase.

- 3.2.20 Prior use of ketoconazole for the purposes of prostate cancer therapy for greater than 1 month
- 3.2.21 Known history of HIV.
The effects of J591 are unknown in this population. Furthermore, ketoconazole has many well-described drug-drug interactions which could affect antiviral therapy. If necessary, this population will be studied separately.
- 3.2.22 Currently active other malignancy other than non-melanoma skin cancer.
Patients are considered not to have “currently active” malignancy if they have completed any necessary therapy and are considered by their physician to be at less than 30% risk of relapse.
 - Known history of known myelodysplastic syndrome
- 3.2.23 Adrenal hormone inhibitors (other than ketoconazole) within 4 weeks prior to study enrollment.
- 3.2.24 Finasteride (Propecia® or Proscar®) or dutasteride (Avodart®) within 4 weeks of enrollment.
- 3.2.25 Patients on corticosteroids prior to enrollment must have either discontinued and shown biochemical progression or have biochemical progression on a stable dose

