9.1.1 Adrenal Androgen Levels

Serum levels of adrenal androgen levels will be obtained at screening (any time following consent and prior to therapy initiation on C1D1), Cycle 2 Day 1, and at the

time of PSA progression. Collect 10 mL of peripheral blood in a yellow (SST) or red top tube. Label samples with the unique sample number that will be provided by the Weill Cornell Medical College study coordinator to ensure that laboratory personnel will be blinded to subject and clinical data.

Please refer to the Lab Manual for further details on collecting, handling and shipping of adrenal androgen samples.

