¹ Baseline radiographic evaluation should be performed within one month of enrollment (or following enrollment as part of screening). Subsequent scans (CT/MRI abd/pelvis, CXR (or CT chest), and bone scan) should be performed every 6 months until PSA progression, then every three months thereafter unless clinically indicated sooner.

² CBC repeated twice a week when platelets <25,000/mm³ and/or ANC <500/mm³

³ CBC's not associated with study visits may be performed at any CLIA certified laboratory

⁴ The same lab should be used for all study PSA's if possible

⁵ CTC counts via CellSearch (using kit) at C1D1 prior to ketoconazole, C2D1 (prior to Lu-J591), C3D1, at the time of PSA progression, and at end of study. Additional blood samples for CTC analysis for research will be drawn at C1D1 prior to treatment and at end of study

⁶ Adrenal hormone levels should be drawn prior to starting treatment on Cycle 1, Day 1, 1 month, and at PSA progression

⁷ Starting after C1D1 assessment and blood draw until toxicity, investigator, or patient decision as per Sections 5.2.1, 5.2.2, 6.1. Distribute medication diary at the beginning of each cycle.

⁸ Visit 3 (C2D1): Targeted physical exams can be completed the day prior to the scheduled J591 infusion date.

⁹ All references to targeted physical exams throughout the protocol include a heart and lung examination, as well as evaluation of any abnormalities found during the complete physical exam performed at screening

¹⁰ Vital signs include temperature, heart rate, blood pressure, and respiratory rate.

¹¹ The End of Study Visit occurs when patient shows evidence of metastatic disease. Patient remains on trial until documented metastatic disease. In addition to scans a biopsy can be performed to prove metastatic disease. Patient can receive additional therapy prior to showing metastatic disease and still remain on trial. Site will be asked for information regarding the additional therapy in the case report forms.

¹² In the event that the J591 infusion is delayed, cycle 1 will be extended until the date of the J591 infusion. The date of the J591 infusion will be considered Cycle 2, Day 1.

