13.4 Analysis of Secondary & Exploratory Endpoints

Secondary endpoints include biochemical (PSA) response rate, duration of PSA response, biochemical (PSA) progression, time to biochemical (PSA) progression, time to biochemical (PSA) progression above baseline, overall survival, and toxicity. We anticipate that the 95% confidence interval around the PSA response rate will be within $\pm 9\%$ of the true value for Arm 1 and within $\pm 15\%$ of the true value for Arm 2. Time to biochemical (PSA) progression, time to biochemical (PSA) progression above baseline, median MFS-time, and overall survival will be estimated using the Kaplan-Meier method, and 95% confidence intervals will be calculated using Greenwood's formula.

The frequency of subjects experiencing toxicities will be tabulated. Toxicities will be assessed and graded according to CTCAE v. 4.0 terminology. Exact 95% confidence intervals around the toxicity proportions will be calculated to assess the precision of the obtained estimates.

Imaging studies: The possibility of identifying sites of metastatic disease not apparent on conventional imaging (CT/MRI abdomen/pelvis, bone scan, and CXR) will be confirmed with serial imaging. Any potential metastatic site on J591 imaging will be followed over time by conventional imaging. Sites of disease appearing on J591 scan and subsequently confirmed by conventional imaging will be labeled as positive. Any site apparent on J591 scan that is subsequently biopsied as part of standard care and confirmed to be metastatic prostate cancer will be labeled as definite. Sites of disease appearing on J591 scan without any corroborating evidence (conventional imaging or biopsy) will be labeled as possible.

Adrenal hormonal levels: Baseline adrenal hormonal levels will be categorized by median baseline levels found in CALGB 9583 (60, 61). In addition, as this may be a different patient population, we will analyze by median as well as quartiles. We will correlate levels with time to radiographic metastatic disease as well as PSA response and overall survival. Changes in adrenal hormone levels will be analyzed with time (baseline, 1 month, 6 months, at progression).

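### The adrenal-androgen prognostic analysis pools all men, although eligibility admits some whose baseline level may already be lowered by prior ketoconazole or a continuing corticosteroid

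*Combined protocol and SAP*

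**What the plan says.** Section 1.2 lists the prognostic value of baseline adrenal hormones as a secondary objective. Section 2.4.1 gives the aim as confirming a published finding: "we plan to prospective assess and validate these results in men with biochemically progressive castrate resistant prostate cancer". The first planned comparison is of responders with non-responders: "we will compare the median baseline androgen levels in those with a PSA response vs those without". Section 13.4 adds cut-points, first external and then the trial's own median and quartiles: "Baseline adrenal hormonal levels will be categorized by median baseline levels found in CALGB 9583". Levels are related to time to radiographic metastasis, PSA response and overall survival, and changes from baseline are also analysed.

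Three criteria in section 3.2 bear on what a baseline level means:

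- 3.2.20 excludes "Prior use of ketoconazole for the purposes of prostate cancer therapy for greater than 1 month", so shorter use is allowed.
- 3.2.23 sets a washout but exempts one drug: "Adrenal hormone inhibitors (other than ketoconazole) within 4 weeks prior to study enrollment".
- 3.2.25 reads "Patients on corticosteroids prior to enrollment must have either discontinued and shown biochemical progression or have biochemical progression on a stable dose", so a continuing stable dose is allowed.

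The baseline sample is timed only against the start of study therapy. The footnote to the calendar in section 10 says "Adrenal hormone levels should be drawn prior to starting treatment on Cycle 1, Day 1", and section 9.1.1 allows any time between consent and that point.

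**The concern.** The analysis treats the baseline level as a feature of the patient's disease and endocrine state. Where a man has recently taken a drug that lowers adrenal androgens, the measured level partly reflects the drug. Section 2.4.1 itself says that ketoconazole is commonly used to target adrenal androgens, and section 7.1.2 lists adrenal suppression among its risks. For corticosteroids the same expectation comes from general pharmacology, not from the documents.

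Two errors can follow, and they run in different directions. If exposure is unrelated to outcome, it adds noise and weakens a real association. If exposed men have a different prognosis, it shifts the association, and a shift towards low level with poor outcome could be read as confirmation. A cut-point fixed from another trial adds to this, because lowered values fall below it whatever the man's untreated level. The baseline-to-1-month change is also blunted in men whose baseline is already lowered.

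**Working it through.** The plan states no sample size, power or precision for this analysis, so there is no figure of its own to reproduce. The check has a textual part and an illustrative part.

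**Text.** Sections 2.4.1, 9.1.1 and 13.4 contain no exclusion, adjustment, stratification or sensitivity analysis for prior ketoconazole or corticosteroids. The visit 2 instruction in section 10.1 against taking drug before the Day 1 draw is attached to the newly filled study prescriptions. It does not deal with a long-term steroid or with ketoconazole taken before the study. Exposure data do exist: section 10.1 collects previous hormonal drugs with doses and dates, and concurrent medications, at screening.

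**Size.** Inputs: about 50 evaluable men (section 13.2). Everything else is assumed, because the documents do not give it: exposed share f of 5%, 10% or 30%, and a downward shift d of 1 or 2 SD on the log scale.

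*Dilution.* Let the log level have SD 1 in unexposed men, with exposure independent of untreated level and outcome. The observed variance is 1 + f(1-f)d², so the correlation with outcome is multiplied by 1/√(1 + f(1-f)d²).

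| f | exposed men of 50 | d = 1 | d = 2 |
|---|---|---|---|
| 5% | 2.5 | 1/√1.0475 = 0.98 | 1/√1.19 = 0.92 |
| 10% | 5 | 1/√1.09 = 0.96 | 1/√1.36 = 0.86 |
| 30% | 15 | 1/√1.21 = 0.91 | 1/√1.84 = 0.74 |

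The information lost is one minus the square of the factor. It is 1 - 1/1.09 = 8% at f = 10%, d = 1, and 1 - 1/1.84 = 46% at f = 30%, d = 2.

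*Make-up of the low group.* Take a fixed cut at the unexposed median. The exposed share of the low group is fΦ(d)/[fΦ(d) + 0.5(1-f)].

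- f = 10%, d = 1: 0.0841/(0.0841 + 0.45) = 16%.
- f = 30%, d = 2: 0.293/(0.293 + 0.35) = 46%.

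*Distortion, only if prognosis differs.* Suppose there is no androgen effect, unexposed men respond at 50%, and exposed men respond at 30% (mild case) or 20% (severe case).

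- Mild (f = 10%, d = 1): exposed men are 15.8% of the low and 3.4% of the high group. Response is 0.50 - 0.158×0.20 = 0.468 and 0.50 - 0.034×0.20 = 0.493. The high-versus-low odds ratio is (0.493/0.507)/(0.468/0.532) = 1.1.
- Severe (f = 30%, d = 2): exposed men are 45.6% and 1.9%. Response is 0.363 and 0.494, and the odds ratio is (0.494/0.506)/(0.363/0.637) = 1.7.
- With f = 5%, d = 1 and 30% response in exposed men, it is about 1.05.

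*Cross-check with a simpler model.* Let true response be 60% for high and 30% for low androgen, half the men truly low, and every exposed man read as low. The observed low-group response is (0.5×0.30 + 0.5f×0.60)/(0.5 + 0.5f). The true 30-point difference becomes 28.6 points at f = 5%, 27.3 at 10% and 23.1 at 30%. With 50 men and a two-sided 5% test, power falls from 57% to 53%, 49% and 34%. The direction agrees.

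**The case against.** The strongest reply is that nothing here shows the exposed group to be more than a handful. Ketoconazole exposure is capped at one month, and study drug is kept away from the baseline draw, so only men with a short earlier course remain. This stands: the share may well be small, and at 5% little changes.

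The corticosteroid effect is not documented. The hydrocortisone taper in section 6 concerns study hydrocortisone, and section 7.1.3 does not list adrenal suppression. Criterion 3.2.25 gives no steroid type, route or dose, so a 1-2 SD shift cannot be checked. This also stands; that half rests on general pharmacology.

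A reader might infer that exposed men have failed an extra line of treatment and must do worse. The documents do not support that. Criterion 3.2.25 does not say that the steroid was given for cancer, and neither 3.2.20 nor 3.2.23 requires progression on ketoconazole. The distorted odds ratios above are therefore conditional. They are also small beside sampling error: with about 12.5 men per cell, the 95% interval around an odds ratio of 1 is exp(±1.96×√(4/12.5)), or about 0.33 to 3.0.

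A reader might also infer that the all-men analysis fails as a validation. That cannot be settled, because the documents do not say whether CALGB 9583 admitted such men. If it did, pooling all men is the closer replication. For this reason the restricted analysis should accompany the all-men results and not replace them.

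What the reply does not answer is that the stated analysis would class a drug-lowered level as low, with no rule to detect or allow for it.

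**Conclusion.** The concern holds in a limited form. Eligibility permits drug-lowered baseline values, the protocol itself supplies the mechanism for ketoconazole, and the planned analysis ignores the exposure. The likely effect is dilution: a factor of 0.98 on the correlation at 5% exposed and a 1 SD shift, and 0.96 to 0.74 at 10-30% exposed and a 1-2 SD shift. Distortion is possible if exposed men differ in prognosis, but neither its presence nor its direction can be established from the documents. The share, shift and response rates are all assumptions. The primary endpoint, the randomised comparison and the safety analyses are untouched. It is worth settling in advance because the remedy is cheap and a choice made after seeing the data would be open to question.

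**What to change.** In section 13.4, with a matching sentence in 2.4.1:

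1. Define an indicator for systemic corticosteroid or ketoconazole use at the baseline draw or in the 4 weeks before it. The window follows the one that 3.2.23 uses for other adrenal inhibitors. Derive it from the previous-therapy and concomitant-medication data already collected, and report how many men are exposed.
2. Include the indicator as a term, or stratify by it, in the prognostic and change-from-baseline analyses. Stratification suits the comparison of medians. With the level as a continuous variable, the term absorbs a constant shift.
3. Report the same analyses in unexposed men only, alongside the all-men results. If only two or three men are exposed, the term will be poorly estimated and this comparison carries the check.

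Before finalising, confirm that the forms capture a steroid stopped shortly before consent. The cost is one model term and a smaller sample in the unexposed-only version. Men exposed earlier than 4 weeks count as unexposed, which should be stated. Eligibility, treatment and visits are unchanged.
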